2.2 Data sources

The data used in this study will come from data entered onto the following Case Report Forms (CRFs):

Visit	CRF reference	Version No/Effective date	
		Version No	Effective date
Training Screening	Screening – Training	1.0	6 April 2010
Training Baseline	Baseline- Training	1.0	6 April 2010
US for training	Ultrasound CRF	2.0	3 June 2010
Screening	Screening – Clinical	2.0	4 June 2010
Baseline	Baseline (Visit 1)- Clinical	2.0	20 September 2011
Baseline	Baseline (Visit 1)- EQ-5D	n/a	EuroQol 1990
< 2 weeks	Biopsy CRF	2.0	20 September 2011
< 2 weeks	Ultrasound CRF	2.0	3 June 2010
2 weeks	Two Weeks (Visit 2) – Clinical	2.0	20 September 2011
2 weeks	Two Weeks (Visit 2) – EQ-5D	n/a	EuroQol 1990
6 months	Six Months (Visit 3) – Clinical	2.0	20 September 2011
6 months	Six Months (Visit 3) – EQ-5D	n/a	EuroQol 1990
From consent to last visit	Adverse Event/Reaction reporting form	3.0	20 September 2011

This data will be stored on the Sheffield CTRU database (PROSPECT). Images from US and TAB will be stored on the Oxford database and will be made available for subsequent expert review and assessment of inter-observer agreement.

2.3 Protocol Deviations

The following are considered major deviations:

1. High dose steroids started more than 2 weeks before presentation
2. TAB not performed within 10 days of starting high dose steroids
3. US either not performed or performed after TAB

2.4 Analysis populations

Analyses will be conducted on the following groups of patients:

Name	Patients included
Training phase	
Training cases	All patients who enter into the training (pre-) phase of the study
Main study	
Primary analysis	All patients who did not deviate from the protocol, as defined in section 2.3, and for whom a clinical diagnosis has been made.
Per-protocol analysis	The subset of the primary analysis population for whom TAB was undertaken within 7 days of commencement of steroids
US/TAB agreement analysis	All patients who did not deviate from the protocol, as defined in section 2.3.
US/TAB agreement – per-protocol analysis	The subset of the US/TAB agreement analysis population for whom TAB was undertaken within 7 days of commencement of steroids.

If sufficient data are available, a separate analysis will be performed for patients in whom the TAB was more than 10 days after high dose steroids, with specific attention paid to those who were delayed for clinical reasons.

2.5 Data Management

A Data Management Plan (DMP) agreed by the CTRU and TMG will define the procedures for data entry, cleaning and validation

3 Outline of analyses

3.1 General considerations

Data will be reported and presented according to the STARD statement (Bossuyt et al 2003).

Complete details of data derivations and methods of handling multiplicity, multi-centre data and missing data are covered in section 4. No interim analyses or early stopping are planned.

All summaries will be provided on the complete case patient set unless otherwise stated

All tables will present summary statistics defined by the nature of the measurement. Summaries of continuous variables will comprise the number of observations used and either
i) mean, median, standard deviation, minimum and maximum, or
ii) median, inter-quartile range, minimum and maximum
as appropriate for the distributional form of the data. Summaries of categorical variables will comprise the number of observations used, and the number and percentage of observations in each category.

[figure not shown]
All statistical tests will be two-tailed with alpha = 0.05, and all confidence intervals will be two-sided, 95% intervals, unless one-sided tests of joint hypotheses are specifically stated.

3.2 Disposition and data completeness

The flow of patients to the various stages will be summarised by the following:

Enrolment	The number of patients screened for entry, the number of patients entered, the number of patients not entered with reasons, the diagnosis (consistent with GCA, not consistent with GCA, not available) from TAB, the diagnosis from US, the number of patients who discontinued at Visit 2 (two weeks) and Visit 3 (6 months), and the reference diagnosis (as described in the flow diagram below).
------------------	---

Patient recruitment and follow up with data collection

[figure not shown]

Figure 1 Algorithm for study patients

3.3 Demographics and baseline characteristics

The following summaries will be presented:

Demographics	Treatment centre, age at baseline, gender, ethnic group, current smoking status and smoking history.
Presenting and evolving medical history and conditions	The proportion of patients with each current condition at presentation, 2 weeks and 6 months.
Presenting and evolving symptoms	The proportion of patients with each symptom at presentation, 2 weeks and 6 months.
Physical and evolving examination	The proportion of patients with each abnormal feature at presentation, 2 weeks and 6 months.
Initial diagnosis and treatment	The certainty of GCA diagnosis, the proportion of patients taking steroids, and the proportion of patients taking immunosuppressants.

Should a patient transfer between centres during the study, the “centre” defined in the analysis is the place at which the patient underwent US.

3.4 Efficacy

3.4.1 Accuracy of US and TAB in relation to reference diagnosis (primary endpoint)

The principal outcome is the performance of US and TAB in relation to the reference ('gold-standard') diagnosis of GCA. The reference diagnosis will be reached as specified in the study protocol.

The following summaries will be presented

TAB	The cross-tabulation of diagnosis by TAB against reference diagnosis, together with the sensitivity, specificity, and associated 95% confidence intervals
US	The cross-tabulation of diagnosis by US against reference diagnosis, together with the sensitivity, specificity, and associated 95% confidence intervals
TAB v US	The cross tabulation of diagnosis by TAB against the diagnosis by US, overall and by final reference diagnosis, together with Kappa statistic and the McNemar test

The kappa statistic will be used to assess agreement between TAB and US, and McNemar’s test will be used to detect systematic discordance i.e. whether one method is more or less likely to diagnose (Fleiss *et al* 2003). Rectangular confidence intervals and the McNemar test statistics will be calculated using the exact Binomial methods.

The performance of US will be evaluated as defined in the protocol using a one-sided rectangular confidence region for sensitivity > TAB and specificity > 0.83 with a 5% type I error rate.

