2.1 Sample Size and Power

A sample of 402 patients provides 90% power at a 5% type I error rate to test the joint hypothesis that

- (i) US has greater sensitivity than TAB, based on detecting a sensitivity of 76% for TAB and 87% sensitivity for US; and
- (ii) The specificity of US is no less than 83%, based on an expected specificity of 96%

The postulated sensitivity and specificity figures are based on the meta-analysis by Karassa et al (2005). This sample size will allow estimation of a one-sided rectangular confidence region for ultrasound false and true positive fractions, assuming 80% prevalence of GCA in patients having a biopsy for suspected GCA, with the sample size inflated ($\gamma=0.1$) due to uncertainty in the proportion of cases/controls in a cohort design (Pepe, 2003).

In order to allow for losses to follow-up the original plan was to recruit 430 participants to the study. It was anticipated that most losses to follow-up will occur in recruited participants not having both ultrasound and biopsy at their appointed time within 7 days of starting steroids. Previous experience of observational studies in PMR (Hutchings et al 2007) suggest no further losses at the

week 2 assessment and 4% at the 6 month assessment. However, the primary outcome (reference standard diagnosis) can be derived in participants who do not complete the 6 month assessment. These assumptions will be checked using early monitoring of recruitment and follow-up rates, with recruitment targets modified as necessary. After monitoring the actual recruitment and withdrawals it was found that the withdrawal rate was slightly higher than expected. It was decided to change the target recruitment figure to 435-445.

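### The primary rule for 'US more sensitive than TAB' rests on a region for US alone; how TAB's estimated sensitivity enters is not fixed, so the 5% error rate is not assured

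*SAP*

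**What the plan says.** SAP section 2.1 sets a joint hypothesis: "A sample of 402 patients provides 90% power at a 5% type I error rate to test the joint hypothesis that" two things hold. The first is comparative: "US has greater sensitivity than TAB, based on detecting a sensitivity of 76% for TAB and 87% sensitivity for US". The second is against a constant: "The specificity of US is no less than 83%, based on an expected specificity of 96" per cent. The same section names the aim of the sample as "estimation of a one-sided rectangular confidence region for ultrasound false and true positive fractions". It takes the prevalence of GCA as 80% and adds an inflation (gamma = 0.1) for the uncertain split of cases and non-cases.

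Section 3.4.1 gives the decision rule. It refers to the protocol for the definition and says that US will be evaluated "using a one-sided rectangular confidence region for sensitivity > TAB and specificity > 0.83 with a 5% type I error rate". On calculation it says: "Rectangular confidence intervals and the McNemar test statistics will be calculated using the exact Binomial methods".

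The same section cross-tabulates TAB against US, overall and by final reference diagnosis, with kappa and McNemar's test. The stated purpose of McNemar's test is to detect systematic discordance. Section 3.1 makes tests two-tailed at 0.05 unless a one-sided joint test is specifically stated. Section 1.4 says that every patient is scheduled for both tests, so the comparison is paired.

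**The concern.** The two halves of the rule differ in kind. For specificity, an exact lower limit for US is compared with 0.83 and the error rate is the nominal one. For sensitivity, the comparator is another test measured in the same patients. A binomial limit for US carries neither TAB's sampling error nor the pairing.

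The text leaves two natural readings: compare the US lower limit with TAB's observed sensitivity, or with the planning value of 76%. The first has an error rate that depends on how strongly the two tests agree within GCA patients. The second does not test US against TAB unless TAB's true sensitivity happens to be 76%. The two can also give opposite answers on the same data, and nothing in the SAP prevents the choice from being made after the results are seen. This is half of the trial's primary claim.

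**Working it through.** **Inputs from the SAP (2.1, 3.4.1).** N = 402; prevalence 80%, so about 0.8 × 402 = 322 cases and 80 non-cases; sensitivities 76% (TAB) and 87% (US); specificity 96% against 83%; joint one-sided error 5%; power 90%; exact binomial limits.

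**Assumptions.** The SAP does not give the level of each side of the rectangle. I take α* = 1 − √0.95 = 0.0253 and β* = 1 − √0.90 = 0.0513 (z = 1.955 and 1.632), and also show a 5% side. The SAP gives no within-patient correlation φ between the tests among cases, so I use 0 to 0.8.

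**The plan's own figure.**
- One-sample formula, TAB fixed at 0.76: cases = [(1.955√(0.76×0.24) + 1.632√(0.87×0.13))/0.11]² = 158.2. Non-cases = [(1.955√(0.83×0.17) + 1.632√(0.96×0.04))/0.13]² = 65.7. Non-cases drive N: 65.7/0.2 = 329 before inflation. With gamma = 0.1 this becomes 377–380 (one tail) or 392–396 (two tails).
- Paired formula, tests independent given GCA: discordance 0.87×0.24 + 0.13×0.76 = 0.2088 + 0.0988 = 0.3076. Cases = [(1.955√0.3076 + 1.632√(0.3076 − 0.11²))/0.11]² = 321.2, and 321.2/0.8 = 401.4, so 402. This leaves out gamma; with it, N is about 415–416.

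Neither route settles which comparison was planned.

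**Reading 1: US lower limit against observed TAB sensitivity, true sensitivities equal.** The rule requires the observed difference to exceed roughly z·SE(US), but the difference has standard error SE(US)·√(2(1 − φ)). The false-positive rate is therefore about 1 − Φ(1.955/√(2(1 − φ))). This equals the nominal 2.53% only at φ = 0.5; it is higher below and lower above. Simulation with exact limits, 322 cases, both sensitivities 76%:

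| φ | 2.53% side | 5% side | Exact McNemar at 2.53% |
|---|---|---|---|
| 0 | 7.4% | 11% | 2.0% |
| 0.2 | 5.2% | 8.4% | 2.0% |
| 0.4 | 3.1% | 5.6% | 2.0% |
| 0.5 | 2.0% | 4.1% | 1.9% |
| 0.6 | 1.1% | 2.6% | 1.8% |
| 0.8 | 0.07% | 0.3% | 1.5% |

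At 87% for both tests the 2.53% column runs from 7.0% to 0.06%, and McNemar from 2.0% to 1.4%.

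The joint claim also needs the specificity criterion. With 80 non-cases and true specificity 96% that is met with probability 95.9%, so the joint false claim at φ = 0 is 0.074 × 0.959 = 7.1%, and at φ = 0.2 it is 0.052 × 0.959 = 5.0%.

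**Reading 2: US lower limit against a fixed 0.76.** The exact 2.53% limit exceeds 0.76 once US detects at least 260 of 322 cases. When both tests have the same true sensitivity:

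| True sensitivity, both tests | P(US declared better) |
|---|---|
| 76% | 2.5% |
| 78% | 13% |
| 80% | 40% |
| 82% | 75% |
| 84% | 95% |
| 87% | 99.9% |

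Conversely, if US is 60% and TAB 49%, the same 11-point advantage, US is essentially never declared better.

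**Power of the paired test at 402.** One-sided exact McNemar at 2.53%, 76% against 87%: 94.2% under conditional independence, 99.2% if 5% of cases are TAB-positive and US-negative, and 89.2% if 13% are, the largest value possible when US misses 13%. Joint power under independence is 0.942 × 0.959 = 90%; at the 13% extreme it is 0.892 × 0.959 = 86%.

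**The case against.** - **The SAP defers to the protocol, which is not at hand.** It may define the comparison. This stands as a limit: that the region covers US alone is the natural reading of 2.1 and 3.4.1 together, not an explicit statement of how TAB is handled. It does not remove the problem, because the SAP itself names the fractions and the exact binomial method, and neither fits a paired comparison.
- **The right test is already planned.** McNemar's test by final reference diagnosis is, among reference-positive patients, the paired comparison of sensitivities. A two-tailed test at 0.05 also puts 2.5% in each direction, almost the component level. This is a fair point and makes the repair small. But the section gives the test a descriptive role and then assigns the decision to the region.
- **The error is not always inflated.** True. Under reading 1 with a 2.53% side, the rule is conservative from φ of about 0.45–0.5 upwards, and the sensitivity error exceeds 5% only below about 0.2. Both tests examine temporal arteries, so independence is not an obvious base case.
- **The largest figure is an extreme.** The 99.9% needs reading 2 and a true TAB sensitivity 11 points above the planning value. At 2 points above it, the figure is 13%.

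A reader might also infer from the match at 402 that the sample size can only have come from a paired calculation, so that the analysis departs from it. The documents do not support that: the match omits the stated gamma inflation, and the one-sample route with gamma over two tails comes within 3% of 402.

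**Conclusion.** The point holds as a defect in the decision rule. The SAP poses a paired comparative hypothesis, describes a region for US only, and does not say how TAB's estimated sensitivity enters it or connect the paired test to the conclusion. On either natural reading the stated 5% is not assured for 'US > TAB'. Against observed TAB, the sensitivity error runs from 7.4% down to under 0.1%, depending on a correlation that the SAP does not give. Against a fixed 0.76, the error is nominal only if TAB's true sensitivity is 76%, and it rises steeply above that.

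The figures assume 322 cases, a 2.53% side and Clopper-Pearson limits. The reading-1 rates depend little on the number of cases; the reading-2 rates depend on it strongly. It would go too far to say that the rule is always anti-conservative, that the SAP explicitly ignores TAB's error, or that 402 is wrong. Because this is the primary rule, it should be settled before the data are analysed.

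**What to change.** Replace the last sentence of SAP 3.4.1 with a rule of this form:

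- Criterion (i): in reference-positive patients, the one-sided exact McNemar test of US+/TAB− against US−/TAB+ is significant at 1 − √0.95 = 2.53%, reported with a one-sided lower limit for the paired difference in sensitivity.
- Criterion (ii): the one-sided exact lower limit of US specificity, at the same level, exceeds 0.83.
- Success requires both.

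Align the description of the region in 2.1 with this and check it against the protocol's definition. Redrawing the rectangle with the sensitivity difference on one axis is optional.

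The cost is wording only: the data and the exact McNemar test are already in the plan. At 402 the rule keeps about 90% joint power under conditional independence and more if the tests agree positively. It falls below that, to about 86% at the extreme, only if the tests are negatively dependent among GCA patients.

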3.4.2 Performance of US and TAB in relation to patient & disease characteristics

Several additional analyses are planned around the accuracy of US and TAB in relation to different characteristics of the disease and subgroups of patient.

Analyses will be carried out using logistic regression in which the outcome is the reference diagnosis. The performance of US across each characteristic will be assessed, initially one characteristic at a time, by fitting the US diagnosis, the characteristic and their interaction term. A receiver-operator characteristic (ROC) curve will be produced to assess the sensitivity and specificity across different levels of the covariate. The same procedure will be used to assess the performance of TAB.

Following on from this, further modelling will be undertaken to evaluate different strategies for the detection of GCA. The performance of the following strategies will be assessed:

1. *Standard diagnosis (“how does the standard method perform?”)*

1a. TAB alone

1b. TAB plus additional potential prognostic factors collected at baseline (e.g. age, history, BVAS)

2. *Experimental diagnosis (“how do the standard and test methods perform together?”)*

2a. TAB plus US (independently) alone

2b. TAB plus US (either/or positive) alone

2c. TAB plus US (interaction) alone

2d. TAB plus US (independently), plus additional baseline factors

- 2e. TAB plus US (either/or positive), plus additional baseline factors
- 2f. TAB plus US (interaction) , plus additional baseline factors

3. *Reduced-experimental diagnosis (“is a TAB always necessary?”)*

- 3a. US alone
- 3b. US plus additional baseline factors
- 3c. US (+ vs -) plus TAB (+ vs – in US -) alone
- 3d. US (+ vs -) plus TAB (+ vs – in US -), plus additional baseline factors

Models will be built using logistic regression, with diagnostic ability assessed by sensitivity, specificity and the c-statistic.

Depending on the level of agreement and the number of positive cases, some of the analyses may not be possible due to collinearity. Special care will be taken to avoid overfitting and sparse cells.

Models will be internally validated using bootstrap methods to assess reproducibility.

Accuracy of US in relation to scan findings

The prevalence of the following specific findings will be tabulated:

3.4.3 Accuracy with respect to timing of US & TAB

The accuracy and agreement in regards to the timing of the US and TAB will be assessed. Two durations will be calculated:

Duration 1: From starting steroids to performing the US scan

Duration 2: From the US scan to having the TAB

TAB versus time	The agreement between diagnosis by TAB and reference diagnosis, by duration from starting steroids to TAB (duration 1 + duration 2).
US versus time	The agreement between diagnosis by US and reference diagnosis, by duration from starting steroids commencing to US.

Duration will be calculated in whole days and groupings will be made with attention to ensuring a reasonable number within each category. This analysis will include all entered patients, regardless of whether or not their TAB was within 8 days.

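### The timing analysis in SAP 3.4.3 lists agreement with the reference by day group; sensitivity by days on steroids would answer the question without depending on GCA prevalence

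*SAP*

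**What the plan says.** SAP section 3.4.3 has accuracy in its heading and opens with "The accuracy and agreement in regards to the timing of the US and TAB will be assessed". Its table then lists two outputs. For biopsy: "The agreement between diagnosis by TAB and reference diagnosis, by duration from starting steroids to TAB (duration 1 + duration 2"). For ultrasound: "The agreement between diagnosis by US and reference diagnosis, by duration from starting steroids commencing to US".

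On the time scale it says "Duration will be calculated in whole days and groupings will be made with attention to ensuring a reasonable number within each category". On the population: "This analysis will include all entered patients, regardless of whether or not their TAB was within 8 days". That eight-day figure matches neither the 7-day limit of the per-protocol population (section 2.4) nor the 10-day limit among the major deviations (section 2.3).

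The section does not define agreement, does not list sensitivity or specificity by duration, and names no test or model. Section 3.4.1, by contrast, lists sensitivity and specificity with 95% confidence intervals for the primary analysis. Section 3.4.2 describes logistic models with a test-by-characteristic interaction, but does not name duration among the characteristics.

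**The concern.** If steroid treatment suppresses the findings that make a test positive, it does so in patients who have GCA. The quantity that should change with days on treatment is therefore sensitivity. Agreement with the reference pools patients with and without GCA, so it also reflects how many of each fall into a day group.

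Delay to biopsy need not be random: section 2.4 itself expects some patients to be delayed for clinical reasons. If the share of GCA differs between early and late patients, agreement can stay flat while sensitivity falls, or shift while sensitivity is constant.

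This matters because 3.4.3 is the only listed analysis that looks at test performance along the time scale on which the 7- and 10-day limits are drawn.

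**Working it through.** **Inputs from the SAP (section 2.1).** N = 402; sensitivity 76% for TAB and 87% for US; expected US specificity 96%; GCA prevalence 80%. Two-sided alpha of 0.05 comes from section 3.1.

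**Assumed, not in the SAP.** TAB specificity 100% (90% as a check), the distribution of days, the size of any fall in sensitivity, and any trend in prevalence.

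**The plan's own figure.** The SAP gives no power or effect size for timing; 402 belongs to the primary joint hypothesis. The one-sided binomial formula for each margin, with alpha 1 − √0.95 and beta 1 − √0.90, gives 159 cases and 66 controls, so 66/0.20 = 330 before inflation. Depending on how the gamma allowance and the error rates are split, the inflated figure is 377 to 401. The planning values are thus a reasonable base for what follows.

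**Step 1: agreement against prevalence, test performance fixed.**

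Percent agreement = prev × sens + (1 − prev) × spec.

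Kappa = (agreement − chance) / (1 − chance), where chance = prev × P(T+) + (1 − prev) × P(T−).

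TAB at 80% prevalence: agreement = 0.8 × 0.76 + 0.2 × 1 = 0.808. P(T+) = 0.608, chance = 0.8 × 0.608 + 0.2 × 0.392 = 0.565, kappa = 0.243/0.435 = 0.56.

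| GCA prevalence | 90% | 80% | 70% | 60% | 50% |
|---|---|---|---|---|---|
| TAB agreement (76%/100%) | 78.4% | 80.8% | 83.2% | 85.6% | 88.0% |
| TAB kappa | 0.39 | 0.56 | 0.66 | 0.72 | 0.76 |

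For US (87%/96%) over the same range, agreement goes from 0.9 × 0.87 + 0.1 × 0.96 = 87.9% to 0.5 × 0.87 + 0.5 × 0.96 = 91.5%, and kappa from 0.55 to 0.83.

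**Step 2: masking.** If an early group has 80% GCA and 76% sensitivity, agreement is 80.8%. If a late group has 50% GCA and 64% sensitivity, agreement is 0.5 × 0.64 + 0.5 = 82.0%. A 12-point loss of sensitivity appears as a rise of 1.2 points. The 30-point difference in prevalence is an illustration.

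**Step 3: simulation.** N = 402, days uniform over 0–10, TAB specificity 100%, sensitivity falling from about 84% to 65%. The comparison is between a logistic model of TAB-positive on continuous days in GCA patients and an assumed unordered chi-square test on agreement in 2, 3 or 4 groups.

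| Prevalence over days 0–10 | Sensitivity on days | Grouped agreement (2/3/4 groups) |
|---|---|---|
| Flat 80% | 71% | 59% / 54% / 49% |
| Falling 95% to 65% | 71% | 19% / 16% / 16% |
| Rising 65% to 95% | 71% | 89% / 88% / 86% |

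The high rejection rates in the last row are partly a prevalence signal, so they do not represent better power.

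At flat prevalence, agreement modelled on continuous days gives 69%. So about 2 points of the 12- to 22-point gap come from the choice of agreement and the rest from unordered grouping. A trend test on sensitivity over four groups also gives 69%. With a steeper fall (88% to 58%) the comparison is 98% against 89–90%. With tightly clustered days and the milder fall it is 44% against 26–31%.

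**Step 4: false signals.** With constant sensitivity and a 30-point prevalence trend, the grouped agreement test rejects in 13–19% of runs instead of 5%. This drops to 6–11% with clustered days, and to 6–9% with uniform days and TAB specificity 90%.

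**Step 5: can specificity be modelled on days?** About 0.20 × 402 = 80 reference-negative patients are expected. At 96% specificity that gives 0.04 × 80 = 3.2 US false positives, and none for TAB at 100%. A day model there is not estimable.

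**The case against.** The opening sentence of 3.4.3 promises accuracy as well as agreement, and 3.4.1 reports accuracy as sensitivity and specificity, so sensitivity by duration is not excluded. This stands: the defect is that the measure is neither listed nor defined. The two rows still say only agreement, and both usual meanings, percent and kappa, move with prevalence.

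A reader might infer that the planned analysis discards much of its power. The documents do not support that. No test is named, so any power figure belongs to an assumed one; at constant prevalence agreement itself costs about 2 points, and an ordered trend recovers nearly all of the rest. The severe loss needs prevalence to fall with delay, and the SAP gives a single prevalence and no trend.

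A reader might also infer that the day groups are chosen to suit the results. The stated rule is that "groupings will be made with attention to ensuring a reasonable number within each category", which looks at counts and not at test results. That is a weak form of data dependence.

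Nor is 3.4.3 the only analysis bearing on the time limits: section 2.4 also has a 7-day per-protocol subset and, if data suffice, a separate analysis of TAB beyond 10 days. These compare populations defined by a limit; neither estimates how sensitivity changes by day.

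**Conclusion.** The point holds as an inexpensive improvement to a secondary analysis. Section 3.4.3 lists an output that mixes test performance with case mix, and no other section models performance by day. That agreement depends on prevalence is arithmetic: over prevalences from 90% to 50%, TAB agreement moves by 9.6 points and kappa by 0.37 with no change in the test, given the SAP's 76% sensitivity and an assumed 100% specificity.

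Whether this would distort the trial's result depends on a prevalence trend with delay, whose existence, size and direction the SAP does not give. The bias could go either way. Without such a trend, the loss comes almost entirely from comparing unordered groups, if that is what is done: the total gap is roughly 8 to 22 points in the uniform-days scenarios. The primary analysis is unaffected.

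**What to change.** In 3.4.3:

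- Among reference-positive patients, fit a logistic regression of TAB-positive on days from steroid start to TAB, and of US-positive on days from steroid start to US, with days continuous or as an ordered trend. Report estimated sensitivity by day with 95% CIs.
- Among reference-negative patients, report specificity by duration group with exact CIs, without a model, because events are too few.
- Fix the display cut points before the data are examined, for example at the SAP's own 7- and 10-day limits, and reconcile the eight-day reference with them.
- Keep the agreement tables as description, and state whether agreement means percent or kappa.

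The cost is SAP wording; the data are already collected. The downside is that the model assumes a smooth day effect, which the grouped tables can check.

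### Read literally, SAP section 3.4.3 lets scans done after biopsy into the US-versus-time table, where scan order could be mistaken for an effect of steroid duration

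*SAP*

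**What the plan says.** SAP section 2.3 lists three major deviations. The first concerns steroid treatment begun too long before the patient presented. The second sets the biopsy window: "TAB not performed within 10 days of starting high dose steroids". The third concerns whether the scan was done and in what order: "US either not performed or performed after TAB".

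Section 2.4 removes all of these patients from the primary population ("All patients who did not deviate from the protocol, as defined in section 2.3, and for whom a clinical diagnosis has been made") and from the US/TAB agreement population. The per-protocol sets tighten the biopsy window to 7 days.

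Section 3.4.3 defines two intervals. Duration 1 runs from steroid start to the scan. The other is "Duration 2: From the US scan to having the TAB". US is then tabulated as "The agreement between diagnosis by US and reference diagnosis, by duration from starting steroids commencing to US", and TAB by the sum of the two durations. The population is fixed in one sentence: "This analysis will include all entered patients, regardless of whether or not their TAB was within 8 days".

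Section 3.4.3 does not exclude, flag or separate scans done after biopsy, and it gives no rule for a negative Duration 2.

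**The concern.** Waiving the biopsy window is sensible when the question is about timing, because late biopsies are needed to see what time does. The sentence goes further than its reason, however. Taking everyone who entered lifts all three deviations, including the third, which concerns the order of the two tests and not the biopsy window.

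For US-versus-time this matters in principle. If the biopsy changes what the scan shows, and if scans after biopsy lie further along the time axis, scan order is confounded with steroid duration. The table has no column from which a reader could tell the two apart.

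The result is also used later. The section on modelling of alternative methods to diagnose GCA (printed as 1.4.6) takes the findings of 3.4.1 to 3.4.5 into the decision model.

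**Working it through.** Section 3.4.3 states no figure of its own, so there is none to reproduce. The planning values in section 2.1 serve only as inputs to an illustration.

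**Step 1. Scan order and the time axis.** Write D1 for steroid start to US, D2 for US to TAB, and T = D1 + D2 for steroid start to TAB.
- Scan before biopsy: D2 ≥ 0, so D1 ≤ T.
- Scan after biopsy: D2 ≤ 0, so D1 ≥ T.

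This holds within a patient. Across patients it gives a tendency at most. A biopsy on day 1 with a scan on day 2 has D1 = 2, whereas a pre-biopsy scan on day 6 has D1 = 6.

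**Step 2. Size in large groups.** From section 2.1: US sensitivity 87%, specificity 96%, GCA prevalence 80%, and the original target of 430 patients. Assumed: no true time effect, three equal duration groups (430/3 ≈ 143), every post-TAB scan in the latest group, 4 to 43 such scans, and a loss of agreement of 10 to 40 points in them.

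- Agreement of US with the reference diagnosis: 0.8 × 0.87 + 0.2 × 0.96 = 0.888.
- Apparent change in the latest group with m such scans and loss d: −m × d / 143.
- Standard error of a difference between two groups: √(2 × 0.888 × 0.112 / 143) = 0.037.

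| Post-TAB scans (m) | Loss 10 points | Loss 20 points | Loss 40 points |
|---|---|---|---|
| 4 | −0.3 | −0.6 | −1.1 |
| 9 | −0.6 | −1.3 | −2.5 |
| 22 | −1.5 | −3.1 | −6.2 |
| 43 | −3.0 | −6.0 | −12.0 |

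Entries are percentage points. One standard error (3.7 points) is exceeded only with 22 scans and a 40-point loss, or with 43 scans and a loss of 20 points or more. With post-TAB scans left out, the apparent change is 0 in this set-up.

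**Step 3. Size in a small late group.** Section 3.4.3 does not fix the groups, so a late group could be much smaller. Assume 20 GCA patients, sensitivity 0.87 in scans before biopsy, and k post-TAB scans with sensitivity s. The group shows ((20 − k) × 0.87 + k × s) / 20.
- k = 3, s = 0.8: (14.79 + 2.40) / 20 = 0.860
- k = 5, s = 0.6: (13.05 + 3.00) / 20 = 0.803
- k = 8, s = 0.4: (10.44 + 3.20) / 20 = 0.682

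The apparent fall runs from about 1 to 19 points. The standard error of one such group is √(0.87 × 0.13 / 20) = 0.075, so the middle case (a fall of 6.8 points) is still within one standard error.

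**Step 4. The day count.** The window is 7 days in section 1.3.3 (exclusion criterion 7) and in the per-protocol sets of section 2.4 ("The subset of the primary analysis population for whom TAB was undertaken within 7 days of commencement of steroids"). It is 10 days in section 2.3 and in the separate late-biopsy analysis of section 2.4. Eight days appears only in section 3.4.3.

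**The case against.** A reader might infer that the SAP sets out to pool post-biopsy scans, and that a false steroid effect on US will follow. The documents do not support this, for several reasons.

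- The sentence may have been meant to waive only the biopsy window. It is loosely worded, and that does not amount to a deliberate plan to pool.
- Section 2.3 gives no reason for the third deviation, and nothing in the SAP describes an effect of biopsy on the scan. Section 3.4.2 lists several temporal sites and the axillary arteries, so losing one segment need not change the overall US diagnosis.
- That post-biopsy scans gather in the late groups is an inference. Step 1 shows that it need not hold across patients, and a 7-day eligibility limit for both tests compresses the axis.
- The two influences can be separated with data already planned. A negative Duration 2 identifies most of these patients, and they must be classified as deviators in any case.
- The number of such scans is unknown. For a major deviation it may well be small.

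All of this stands, and it limits the point to a possible distortion in one secondary table. It does not remove the point: the rule as written is broader than its stated reason, and the table as laid out would not show scan order.

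**Conclusion.** The population rule for US-versus-time should be narrowed. As written it admits scans done after biopsy, and any effect of the biopsy on those scans could be read as an effect of days on steroids.

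The size cannot be settled from the SAP. With few such scans spread over large groups it is negligible. It could be material only if they are numerous or the late groups are small, and if the biopsy does alter the US result. The direction of any such effect is also unknown; the illustration assumes a loss.

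It would be wrong to conclude that the main result is at risk. The primary and agreement populations in section 2.4 exclude these patients, and section 3.4.3 is a secondary analysis with no stated test or threshold. The 8-day figure is a clerical mismatch with little consequence here, since the sentence sets the window aside anyway.

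**What to change.** In section 3.4.3, state the population separately for the two tables.

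- **US-versus-time:** all entered patients with a US, except those scanned after TAB, whatever the interval from steroid start to TAB.
- **TAB-versus-time:** all entered patients with a TAB, whether the scan came before, after or not at all. A later scan cannot affect an earlier biopsy, so nothing is gained by dropping them. Take steroid-to-TAB time directly from the two dates, so that a missing scan or a negative Duration 2 does no harm.
- **Patients scanned after TAB:** list them separately with their US result and reference diagnosis. Identify them by a negative Duration 2 or, where both tests fell on the same day and whole-day durations cannot show the order, by the record of the third deviation.
- **Clerical:** reconcile the 8 days with the 7- and 10-day windows in sections 1.3.3, 2.3 and 2.4.

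The cost is a few sentences and no new data. A few scans leave one secondary table.
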